10.3. Exploratory endpoints

- Frequency of p17, p24, Nef and RT-specific CD4+ T cells to other HIV clades expressing IL-2 and/or TNF-α and/or IFN-γ and/or CD40-L, as determined by ICS at Day 44 (two weeks after the second vaccination) and/or at Month 2.
- Frequency of p17, p24, Nef and RT-specific CD8+ T cells expressing IL-2 and/or TNF-α and/or IFN-γ and/or CD40-L, as determined by ICS at Months 0, 2, 6, 7, 12 and at Day 44 (two weeks after the second vaccination). (Amended September 24, 2007)
- Frequency of p17, p24, Nef and RT-specific CD8+ T cells expressing at least 2 cytokines (IL-2 and/or TNF-α and/or IFN-γ and/or CD40-L) equal or above the cut-off at Months 0, 2, 6, 7, 12 and at Day 44 (two weeks after the second vaccination). (Amended September 24, 2007)

10.4. Estimated sample size

As this study is a first evaluation of safety and immunogenicity of the HIV candidate vaccine F4co, no formal sample size determination has been performed.

However, Table 11 presents the precision achieved for estimation of the primary parameters.

Table 11Precision achieved for different estimated proportions and for the
two sample sizes of 10 and 50 subjects [by PASS 2005, 95%
confidence interval of a proportion].

Estimated proportion	Precision N=50	Precision N=10
0.20 or 0.80	0.10	0.20
0.40 or 0.60	0.14	0.30

If we want to compare the three adjuvanted groups in terms of proportion of subjects with a given adverse event or in terms of proportion of responders to a vaccine antigen, the sample size of 50 subjects per group would achieve 80% power to detect around 20-30% difference in proportions with a two-sided alpha level of 0.0167 (Bonferroni's adjustment for 3 comparisons) (see Table 12).

Table 12Difference between 2 groups of 50 subjects that can be detected
with a power of 80% (two-sided alpha of 0.0167 for multiple
comparisons between three groups) (by PASS 2005, two
independent proportions, Fisher's Exact test)

Proportion in group 1	Proportion in group 2	Difference in proportions
0.10	0.38	0.28
0.20	0.52	0.32
0.30	0.63	0.33
0.40	0.73	0.33
0.50	0.82	0.32
0.60	0.89	0.29
0.70	0.95	0.25
0.80	0.99	0.19

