10.7.3. Analysis of safety

The primary analysis will be based on the Total Vaccinated cohort. If the percent of enrolled subjects excluded from the ATP cohort for analysis is more than 5%, a second analysis based on this ATP cohort will be performed to complement the total analysis.

Adverse events

The following parameters will be tabulated per treatment group:

- The percentage of subjects with at least one local AE (solicited and unsolicited), with at least one general AE (solicited and unsolicited) and with any AE during the solicited follow-up period will be tabulated with exact 95% confidence interval (CI) after each vaccine injection and overall.
- The percentage of vaccine injections followed by at least one local AE (solicited and unsolicited), by at least one general AE (solicited and unsolicited) and by any AE will be tabulated, overall vaccination course, with exact 95% CI.
- The percentage of subjects reporting each individual solicited local and general AE during the solicited follow-up period will be tabulated with exact 95% CI.
- The percentage of vaccine injections followed by each individual solicited local and general AE will be tabulated, overall vaccination course, with exact 95% CI.
- The proportion of subjects with at least one report of unsolicited AE classified by the Medical Dictionary for Regulatory Activities (MedDRA) and reported up to 30 days after vaccination will be tabulated with exact 95% CI.

The same tabulations will be done for grade 3 adverse events and/or for adverse events with relationship to vaccination.

Fever will be reported per 0.5°C cumulative increments.

Serious AEs and withdrawal due to AEs will be described in detail.

Haematological and biochemical parameters

The frequency distribution of values below, within and above normal ranges will be tabulated per treatment group at each scheduled time point.

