## 3.4. Methodology for computing CI

All CI will be 2 sided 95% CI.

- The exact 95% CIs for a proportion within a group will be calculated from Proc StatXact [Clopper CJ, Pearson ES. The use of confidence or fiducial limits illustrated in the case of binomial. *Biometrika*. 1934;26:404-413].
- The 95% CI for geometric mean titers/concentrations (GMTs/GMCs) will be obtained within each group separately. The 95% CI for the mean of log-transformed titer/concentration will be first obtained assuming that log-transformed values were normally distributed with unknown variance. The 95% CI for the GMTs/GMCs will be then obtained by exponential-transformation of the 95% CI for the mean of log-transformed titer/concentration.

| gsk
GlaxoSmithKline | Stu                | Idy RAP          |  |
|------------------------|--------------------|------------------|--|
| Study Id: 108706       | Abbreviated Title: | PRO HIV-005      |  |
| Version: Draft version | i ⊠ Final          | Date: 26SEP 2008 |  |

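### Protocol Table 11 overstates precision at proportions of 0.20 or 0.80: it prints 0.10 (N=50) and 0.20 (N=10), where the formula behind its other row gives 0.11 and 0.25

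*Protocol*

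**What the plan says.** Protocol Section 10.4 states that "no formal sample size determination has been performed" and then offers two tables. The first is introduced with the words "Table 11 presents the precision achieved for estimation of the primary parameters". Its caption gives the group sizes, the software and the confidence level ("two sample sizes of 10 and 50 subjects [by PASS 2005, 95"%), but it neither names the interval formula nor defines precision. The two rows, each giving proportion, N=50 and N=10 in that order, read "0.20 or 0.80 0.10 0.20" and "0.40 or 0.60 0.14 0.30".

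The second, Table 12, covers only comparisons between two groups of 50.

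For the analysis itself, Protocol Section 10.7.3 says that adverse-event percentages "will be tabulated with exact 95% confidence interval (CI) after each vaccine injection and overall". SAP Section 3.4 says "All CI will be 2 sided 95% CI" and "The exact 95% CIs for a proportion within a group will be calculated from Proc StatXact", citing Clopper and Pearson. The SAP does not restate Table 11.

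**The concern.** The two rows of Table 11 do not appear to come from the same calculation. With N and the confidence level fixed, a normal-theory half-width depends on the proportion only through the square root of p(1−p), so the rows must stand in a fixed ratio. They do not.

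Table 11 is the only statement of how precisely a single group's primary proportions would be estimated. For the three non-adjuvanted groups of 10 it is the only sample-size information in Section 10.4. A reader who takes the 0.20 at face value would expect an observed 20% to carry an interval of about 0% to 40%. Uncertainty in those groups is materially larger than that.

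**Working it through.** **Inputs.** Proportions 0.20/0.80 and 0.40/0.60, N = 50 and 10, 95% level (Protocol Section 10.4, Table 11); two-sided intervals, z = 1.96 (SAP Section 3.4). Because p(1−p) is symmetric, 0.20 and 0.80 share a half-width, as do 0.40 and 0.60.

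**Step 1: the row that reproduces.** Half-width = 1.96 × √(p(1−p)/N).

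- p = 0.40, N = 50: 1.96 × √(0.24/50) = 0.136; printed 0.14.
- p = 0.40, N = 10: 1.96 × √(0.24/10) = 0.304; printed 0.30.

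**Step 2: the same formula on the other row.**

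- p = 0.20, N = 50: 1.96 × √(0.16/50) = 0.111; printed 0.10.
- p = 0.20, N = 10: 1.96 × √(0.16/10) = 0.248; printed 0.20.

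**Step 3: could another confidence level explain it?** Under the normal formula the ratio of the 0.40 row to the 0.20 row is √(0.24/0.16) = 1.22 for any z. The printed ratios are 0.14/0.10 = 1.40 and 0.30/0.20 = 1.50. Even with the most favourable two-decimal rounding they are 0.135/0.105 = 1.29 and 0.295/0.205 = 1.44. No single level yields both rows.

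**Step 4: could another method explain it?** Half-widths at 95% unless stated:

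| Method | p=0.20, N=50 | p=0.20, N=10 | p=0.40, N=50 | p=0.40, N=10 |
|---|---|---|---|---|
| Printed in Table 11 | 0.10 | 0.20 | 0.14 | 0.30 |
| Normal | 0.111 | 0.248 | 0.136 | 0.304 |
| Normal, continuity-corrected | 0.121 | 0.298 | 0.146 | 0.354 |
| Normal with t quantile | 0.114 | 0.286 | 0.139 | 0.351 |
| Wilson | 0.109 | 0.227 | 0.131 | 0.260 |
| Agresti-Coull | 0.111 | 0.237 | 0.131 | 0.261 |
| Jeffreys | 0.109 | 0.229 | 0.133 | 0.272 |
| Arcsine | 0.110 | 0.232 | 0.134 | 0.285 |
| Mid-p | 0.111 | 0.242 | 0.134 | 0.283 |
| Clopper-Pearson | 0.118 | 0.265 | 0.142 | 0.308 |
| Normal, 90% level | 0.093 | 0.208 | 0.114 | 0.255 |
| Clopper-Pearson, lower arm only | 0.100 | 0.175 | 0.136 | 0.278 |

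No line matches all four printed cells to two decimals.

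**Step 5: size of the discrepancy.**

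- Shortfall relative to the normal half-width: (0.111 − 0.10)/0.111 ≈ 10% at N = 50; (0.248 − 0.20)/0.248 ≈ 19% at N = 10.
- Under the normal formula the printed values imply z = 0.10/√(0.16/50) = 1.77 and 0.20/√(0.16/10) = 1.58, that is, about 92% and 89% confidence.
- N needed for the printed half-widths is 1.96² × 0.16/d²: 61.5 for d = 0.10 and 15.4 for d = 0.20, so about 62 and 16 subjects rather than 50 and 10.
- Exact limits: 10/50 gives 10.0% to 33.7% (0.100 below the estimate, 0.137 above); 2/10 gives 2.5% to 55.6% (0.175 below, 0.356 above).

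**Check on the neighbouring table.** Two-sided Fisher power at n = 50 and alpha 0.0167 for the eight pairs in Table 12 lies between 0.786 and 0.806, so that table reproduces. The problem is confined to one row of Table 11.

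**The case against.** Three arguments run the other way.

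*It may only be coarse rounding.* Rounded to one decimal, the normal half-widths 0.111, 0.248 and 0.304 become 0.1, 0.2 and 0.3, which fits three of the four cells. That may well be how the row arose. But the fourth cell is printed as 0.14, so the table presents two decimals, and at that resolution 0.248 is 0.25. A rounding slip explains the figure without making it correct.

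*The method is not stated, so the normal formula is an inference.* This is fair. The distance from the estimate to the lower Clopper-Pearson limit matches the N=50 column (0.100 and 0.136) and would match N=10 (0.175 and 0.278) if that column alone were rounded to one decimal. This reading needs mixed rounding, misses both N=10 cells at the printed resolution, and ignores the longer upper arm, which is 0.356 for 2/10. It cannot serve as the precision of a two-sided interval.

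*Little depends on it.* This stands. The protocol disclaims a formal sample size calculation. The SAP's result templates print actual interval limits for each group. SAP Section 2.5 records the Month 2 analysis as already performed. It is also true that a symmetric 0.25 describes the planned exact interval poorly at N=10: the normal lower limit would be 0.20 − 0.248 = −0.048. That is a good reason to show the exact limits, but not to leave the row as it is.

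**Conclusion.** The concern holds. The 0.20/0.80 row of Table 11 is wrong as written: 0.10 should be 0.11 at N=50, and 0.20 should be 0.25 at N=10. This takes precision to mean the half-width of a two-sided 95% normal-approximation interval, a reading inferred from the row that reproduces. The finding does not hinge on that choice, since every 95% two-sided method tried gives at least 0.109 and 0.227 for this row.

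The N=50 discrepancy is about 0.01 and of little practical weight. The N=10 discrepancy is about 0.05 and is the one worth correcting. Both err towards overstating precision. The consequence is limited to how the design is described: neither group size was derived from the table, and the planned analyses and reported intervals are unaffected.

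**What to change.** In Protocol Section 10.4, Table 11, restate the 0.20/0.80 row as 0.11 (N=50) and 0.25 (N=10), and label the column as the half-width of the two-sided 95% normal-approximation interval, once the sponsor has confirmed that this was the method used. The 0.40/0.60 row stays as it is.

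It would be useful to add the exact limits, so that the table matches the method in SAP Section 3.4: 10.0% to 33.7% for 10/50 and 2.5% to 55.6% for 2/10, with the mirror images 66.3% to 90.0% for 40/50 and 44.4% to 97.5% for 8/10.

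The cost is two table cells and a method label. The stated precision becomes slightly less favourable; sample size, analyses and reported intervals do not change.

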10.5. Study cohorts to be evaluated

Total Vaccinated cohort

The Total Vaccinated cohort will include all vaccinated subjects.

Thus, the Total Vaccinated cohort for analysis of safety will include all subjects with at least one vaccine administration documented.

The Total Vaccinated cohort for analysis of immunogenicity will include vaccinated subjects for whom data concerning immunogenicity endpoint measures are available.

The Total Vaccinated cohort analysis will be performed per treatment actually administered.

According-To-Protocol (ATP) cohort for analysis of safety

The ATP cohort will include all vaccinated subjects

- who have received at least one dose of study vaccine according to their random assignment
- with sufficient data to perform an analysis of safety (at least one dose with safety follow-up)
- for whom administration route of study vaccines is known
- who have not received a vaccine not specified or forbidden in the protocol
- for whom the randomization code has not been broken.

According To Protocol (ATP) cohort for analysis of immunogenicity

The ATP cohort for analysis of immunogenicity will include all evaluable subjects, (i.e., those meeting all eligibility criteria, complying with the procedures and intervals defined in the protocol, with no elimination criteria during the study) for whom data concerning immunogenicity endpoint measures are available.

10.6. Derived and transformed data

Serology data

- The cut-off values for antibody titers will be defined by the laboratory before the analysis.
- A seronegative subject is a subject whose titer is below the cut-off value.
- A seropositive subject is a subject whose titer is greater than or equal to the cut-off value.
- The seropositivity rate is defined as the percentage of seropositive subjects.
- The Geometric Mean Titers (GMTs) calculations will be performed by taking the anti-log of the mean of the log titer transformations. Antibody titers below the cut-off of the assay will be given an arbitrary value of half the cut-off for the purpose of GMT calculation.

JCS data

- ICS data will be expressed as antigen-specific CD4/CD8 T-cells per million respectively of CD4 or CD8+ T-cells.
- The cut-off will be calculated by taking the 95 percentile of the pre-vaccination data of all subjects.
- A responder is a subject with antigen-specific CD4/CD8 T-cells response greater than or equal to the cut-off value.
- Frequency of CD4/CD8 T-cells expressing cytokines to the fusion protein F4co (all antigens) will be estimated by adding individual frequencies of CD4/CD8 T-cells to each 4 antigens (p17, p24, Nef, RT).

Handling of missing

- For a given subject and a given immunogenicity measurement, missing or nonevaluable measurements will not be replaced.
- For the calculation of percentage of responders to 1, 2, 3 and all 4 antigens, subjects not responding to at least one of the concerned antigen(s) will not be taken into account.
- For the analysis of solicited symptom, missing or non-evaluable measurements will not be replaced. Therefore the analysis of the solicited symptoms based on the total

vaccinated cohort will include only injections with documented safety data (i.e. symptom screen/sheet completed).

• For the analysis of unsolicited adverse events/serious adverse event/concomitant medication, all vaccinated subjects will be considered and subjects who did not report an event will be considered as subjects without an event.

10.7. Final analyses

10.7.1. Analysis of demographics/baseline characteristics

Demographic characteristics (age, gender, race) of each study cohort will be tabulated.

The mean age (plus range and standard deviation) by gender of the enrolled subjects, as a whole, and per group, will be calculated.

10.7.2. Analysis of immunogenicity

The primary analysis will be based on the ATP cohort for analysis of immunogenicity. If the percent of enrolled subjects excluded from this ATP cohort is more than 5%, a second analysis based on the Total Vaccinated cohort will be performed to complement the ATP analysis.

Cell-mediated immune response

For cell-mediated immune response, the following parameters will be tabulated by vaccine groups at months 0, 2, 6, 7, 12 and at day 44 (two weeks after the second vaccination)(Amended September 24, 2007):

- descriptive statistics of the frequency of CD4/CD8 T cell expressing at least two different cytokines (IFN-γ, IL-2, TNF-α,CD40L) to each antigen and to all antigens;
- descriptive statistics of the frequency of CD4/CD8 T cell expressing at least IFN- γ and another cytokine (IL-2, TNF- α , CD40L) to each antigen and to all antigens;
- descriptive statistics of the frequency of CD4/CD8 T cell expressing at least IL-2 and another cytokine (IFN-γ, TNF-α, CD40L) to each antigen and to all antigens;
- descriptive statistics of the frequency of CD4/CD8 T cell expressing at least TNF- α and another cytokine (IFN- γ , IL-2,CD40L) to each antigen and to all antigens;
- descriptive statistics of the frequency of CD4 T cell expressing at least CD40L and another cytokine (IFN- γ , IL-2, TNF- α) to each antigen and to all antigens.

CD4+ T-cells expressing JL-2 and another cytokine

For CD4+ T-cells expressing IL-2 and another cytokine response, the following parameters will be tabulated by vaccine groups at months 0, 2, 6, 7, 12 and at day 44 (two weeks after the second vaccination) (Amended September 24, 2007):

• percentage of responders to each antigen (p17, p24, Nef, RT);

- percentage of responders to at least one antigen (p17, p24, Nef or RT);
- percentage of responders to at least two antigens;
- percentage of responders to at least three antigens;
- percentage of responders to all four antigens (p17, p24, Nef and RT).

CDS+ *T***-cells expressing at least 2 cytokines (IL-2 and/or TNF-\alpha and/or IFN-\gamma and/or CD40-L)**

For CD8+ T-cells expressing at least 2 cytokines, percentage of responders to each antigen (p17, p24, Nef, RT) will be tabulated by vaccine groups at months 0, 2, $\frac{6}{7}$, 12 and at day 44 (two weeks after the second vaccination). (Amended September 24, 2007)

Humoral immune response

For humoral immune response, the following parameters will be tabulated by vaccine groups for each antigen (p17, p24, Nef, RT and F4co) at months 0, 2, 6, 7, 12 and at day 44 (two weeks after the second vaccination) (Amended September 24, 2007):

- Geometric mean titers (GMTs) with 95% confidence intervals (CIs);
- Seropositivity rates with exact 95% CIs.

10.7.3. Analysis of safety

The primary analysis will be based on the Total Vaccinated cohort. If the percent of enrolled subjects excluded from the ATP cohort for analysis is more than 5%, a second analysis based on this ATP cohort will be performed to complement the total analysis.

Adverse events

The following parameters will be tabulated per treatment group:

- The percentage of subjects with at least one local AE (solicited and unsolicited), with at least one general AE (solicited and unsolicited) and with any AE during the solicited follow-up period will be tabulated with exact 95% confidence interval (CI) after each vaccine injection and overall.
- The percentage of vaccine injections followed by at least one local AE (solicited and unsolicited), by at least one general AE (solicited and unsolicited) and by any AE will be tabulated, overall vaccination course, with exact 95% CI.
- The percentage of subjects reporting each individual solicited local and general AE during the solicited follow-up period will be tabulated with exact 95% CI.
- The percentage of vaccine injections followed by each individual solicited local and general AE will be tabulated, overall vaccination course, with exact 95% CI.
- The proportion of subjects with at least one report of unsolicited AE classified by the Medical Dictionary for Regulatory Activities (MedDRA) and reported up to 30 days after vaccination will be tabulated with exact 95% CI.

The same tabulations will be done for grade 3 adverse events and/or for adverse events with relationship to vaccination.

Fever will be reported per 0.5°C cumulative increments.

Serious AEs and withdrawal due to AEs will be described in detail.

Haematological and biochemical parameters

The frequency distribution of values below, within and above normal ranges will be tabulated per treatment group at each scheduled time point.

10.8. Planned interim analyses

Safety interim analyses

Nine Six interim analyses are planned for safety evaluation (see Section 5.6).

These analyses will be performed at the end of the 7-day follow-up period (Days 7, *and* 37 and 187) after each vaccine injection in a subset of 12 subjects and for each vaccine dose (10, 30 and 90 µg).(Amended September 24, 2007)

Analysis will be done on uncleaned and blinded data. Individual data listings of the demographic and safety data (solicited/unsolicited AE, SAE, haematology and biochemistry values) will be provided to the SRT. Tables with the number of subjects responding to each stopping rules will be also provided.

Analyses will be performed by an external statistician if unblinding of data is required. Individual data listings and tables will then be provided to an internal data monitoring committee.

No clinical report will be written.

Final analyses

Final analyses will be performed by groups on cleaned data and in three-two steps.

- A first analysis will be performed when all data up to and including month 2 (immogenicity and safety) will be available.
- A second analysis will be performed when all data up to and including month 7 (immogenicity and safety) will be available.
- A third second analysis will be performed and a clinical report will be written at the completion of the study. (Amended September 24, 2007)

Appendix A World Medical Association Declaration of Helsinki

Recommendations guiding physicians in biomedical research involving human subjects

Adopted by the 18th World Medical Assembly Helsinki, Finland, June 1964

and amended by the 29th World Medical Assembly Tokyo, Japan, October 1975 35th World Medical Assembly Venice, Italy, October 1983 41st World Medical Assembly Hong Kong, September 1989 and the 48th General Assembly Somerset West, Republic of South Africa, October 1996

INTRODUCTION

It is the mission of the physician to safeguard the health of the people. His or her knowledge and conscience are dedicated to the fulfilment of this mission.

The Declaration of Geneva of the World Medical Association binds the physician with the words, "The health of my patient will be my first consideration," and the International Code of Medical Ethics declares that, "A physician shall act only in the patient's interest when providing medical care which might have the effect of weakening the physical and mental condition of the patient."

The purpose of biomedical research involving human subjects must be to improve diagnostic, therapeutic and prophylactic procedures and the understanding of the etiology and pathogenesis of disease.

In current medical practice most diagnostic, therapeutic or prophylactic procedures involve hazards. This applies especially to biomedical research.

Medical progress is based on research which ultimately must rest in part on experimentation involving human subjects.

In the field of biomedical research a fundamental distinction must be recognized between medical research in which the aim is essentially diagnostic or therapeutic for a patient, and medical research, the essential object of which is purely scientific and without implying direct diagnostic or therapeutic value to the person subjected to the research.

Special caution must be exercised in the conduct of research which may affect the environment, and the welfare of animals used for research must be respected.

Because it is essential that the results of laboratory experiments be applied to human beings to further scientific knowledge and to help suffering humanity, the World Medical Association has prepared the following recommendations as a guide to every physician in biomedical research involving human subjects. They should be kept under review in the future. It must be stressed that the standards as drafted are only a guide to physicians all over the world. Physicians are not relieved from criminal, civil and ethical responsibilities under the laws of their own countries.

I. BASIC PRINCIPLES

- 1. Biomedical research involving human subjects must conform to generally accepted scientific principles and should be based on adequately performed laboratory and animal experimentation and on a thorough knowledge of the scientific literature.
- 2. The design and performance of each experimental procedure involving human subjects should be clearly formulated in an experimental protocol which should be transmitted for consideration, comment and guidance to a specially appointed committee independent of the investigator and the sponsor provided that this independent committee is in conformity with the laws and regulations of the country in which the research experiment is performed.
- 3. Biomedical research involving human subjects should be conducted only by scientifically qualified persons and under the supervision of a clinically competent medical person. The responsibility for the human subject must always rest with a medically qualified person and never rest on the subject of research, even though the subject has given his or her consent.
- 4. Biomedical research involving human subjects cannot legitimately be carried out unless the importance of the objective is in proportion to the inherent risk to the subject.
- 5. Every biomedical research project involving human subjects should be preceded by careful assessment of predictable risks in comparison with foreseeable benefits to the subject or to others. Concern for the interests of the subject must always prevail over the interests of science and society.
- 6. The right of the research subject to safeguard his or her integrity must always be respected. Every precaution should be taken to respect the privacy of the subject and to minimize the impact of the study on the subject's physical and mental integrity and on the personality of the subject.
- 7. Physicians should abstain from engaging in research projects involving human subjects unless they are satisfied that the hazards involved are believed to be predictable. Physicians should cease any investigation if the hazards are found to outweigh the potential benefits.
- 8. In publication of the results of his or her research, the physician is obliged to preserve the accuracy of the results. Reports of experimentation not in accordance with the principles laid down in this Declaration should not be accepted for publication.

- 9. In any research on human beings, each potential subject must be adequately informed of the aims, methods, anticipated benefits and potential hazards of the study and the discomfort it may entail. He or she should be informed that he or she is at liberty to abstain from participation in the study and that he or she is free to withdraw his or her consent to participation at any time. The physician should then obtain the subject's freely-given informed consent, preferably in writing.
- 10. When obtaining informed consent for the research project the physician should be particularly cautious if the subject is in a dependent relationship to him or her or may consent under duress. In that case the informed consent should be obtained by a physician who is not engaged in the investigation and who is completely independent of this official relationship.
- 11. In case of legal incompetence, informed consent should be obtained from the legal guardian in accordance with national legislation. Where physical or mental incapacity makes it impossible to obtain informed consent, or when the subject is a minor, permission from the responsible relative replaces that of the subject in accordance with national legislation.

Whenever the minor child is in fact able to give a consent, the minor's consent must be obtained in addition to the consent of the minor's legal guardian.

12. The research protocol should always contain a statement of the ethical considerations involved and should indicate that the principles enunciated in the present Declaration are complied with.

II. MEDICAL RESEARCH COMBINED WITH PROFESSIONAL CARE (Clinical research)

- 1. In the treatment of the sick person, the physician must be free to use a new diagnostic and therapeutic measure, if in his or her judgement it offers hope of saving life, re-establishing health or alleviating suffering.
- 2. The potential benefits, hazards and discomfort of a new method should be weighed against the advantages of the best current diagnostic and therapeutic methods.
- 3. In any medical study, every patient including those of a control group, if any should be assured of the best proven diagnostic and therapeutic method. This does not exclude the use of inert placebo in studies where no proven diagnostic or therapeutic method exists.
- 4. The refusal of the patient to participate in a study must never interfere with the physician--patient relationship.
- 5. If the physician considers it essential not to obtain informed consent, the specific reasons for this proposal should be stated in the experimental protocol for transmission to the independent committee (I, 2).
- 6. The Physician can combine medical research with professional care, the objective being the acquisition of new medical knowledge, only to the extent that medical research is justified by its potential diagnostic or therapeutic value for the patient.

III. NON-THERAPEUTIC BIOMEDICAL RESEARCH INVOLVING HUMAN SUBJECTS (Non-clinical biomedical research)

- 1. In the purely scientific application of medical research carried out on a human being, it is the duty of the physician to remain the protector of the life and health of that person on whom biomedical research is being carried out.
- 2. The subjects should be volunteers either healthy persons or patients for whom the experimental design is not related to the patient's illness.
- 3. The investigator or the investigating team should discontinue the research if in his 1 her or their judgement it may, if continued, be harmful to the individual.

In research on man, the interest of science and society should never take precedence over considerations related to the well being of the subject.

